5.1.2 Concomitant medication date imputation

5.1.2.1 Concomitant medication end date

To impute concomitant end date:

- 1. If the concomitant end date year value is missing, the date uncertainty is too high to impute a rational date. Therefore, if the concomitant end year value is missing or ongoing, the imputed concomitant end date is set to NULL.
- 2. Else, if the concomitant end date month is missing, the imputed end date should be set to the earliest of the (study treatment follow-up period date, 31DECYYYY, date of death).
- 3. If the concomitant end date day is missing, the imputed end date should be set to the earliest of the (study treatment follow-up period date, last day of the month, date of death).

If the imputed concomitant end date is less than the existing concomitant start date, use the concomitant start date as the imputed concomitant end date.

5.1.2.2 Concomitant medication start date

Concomitant treatments with partial start dates will have the date or dates imputed. Partial concomitant treatment start dates are imputed with reference to the first administration of study treatment (TRTSTD) within this study in accordance with the rules outlined below.

		Day	Month	Year
Partial AE Start D	ate	Not used	MON	YYYY
Treatment Start D	ate (TRTSTD)	Not used	TRTM	TRTY
The following ma	atrix explains the lo	gic behind the imp	outation.	
Comparison of month section	MON missing	MON <trtm< td="">MON=TRTM	MON>TRTM	</trtm<>	MON=TRTM	MON>TRTM
YYYY missing	(C)	(C)	(C)	(C)
	Uncertain	Uncertain	Uncertain	Uncertain

Comparison of month section	MON missing	MON <trtm< th="">MON=TRTM	MON>TRTM	</trtm<>	MON=TRTM	MON>TRTM
YYYY <trtm< td="">(D) =	(A) =	(A) =	(A) =	</trtm<>	(D) =	(A) =	(A) =	(A) =
	01JULYYYY	15MONYYYY	15MONYYYY	15MONYYYY
	Before Treatment	Before Treatment	Before Treatment	Before Treatment
	Start	Start	Start	Start
YYYY=TRTY	(C)	(A) =	(C)	(B)
	Uncertain	15MONYYYY	Uncertain	= 01MONYYYY
		Before Treatment		After Treatment
		Start		Start
YYYY>TRTY	(E) =	(B)	(B)	(B)
	01JANYYYY	= 01MONYYYY	= 01MONYYYY	= 01MONYYYY
	After Treatment	After Treatment	After Treatment	After Treatment
	Start	Start	Start	Start

The following table is the legend to the logic matrix.

Relationship	
Before Treatment start	Partial date indicates CMD start date prior to Treatment Start Date in this study
After Treatment start	Partial date indicates CMD start date after Treatment Start Date in this study
Uncertain	Partial date insufficient to determine relationship of CMD start date to Treatment Start Date in this study
Imputation calculation	
NC/Blank Uncertain	No convention
(A) Before Treatment Start	15MONYYYY
(B) After Treatment Start	MAX(01MONYYYY, TRTSTD+1)
(C) Uncertain	IF CMDTYP1C IN (1, 3) THEN TRTSTD-1
	ELSE IF CMDTYP1C IN (. 2) THEN TRTSTD+1
(D) Before Treatment Start	01JULYYYY
(E) After Treatment Start	01JANYYYY

To compute concomitant start date:

- 1. If the concomitant start date year value is missing, the imputed concomitant start date is set to one day prior to study treatment start date.
- 2. If the concomitant start date year value is less than the study treatment start date year value, the concomitant medication started before study treatment. Therefore:
 - a. If the concomitant month is missing, the imputed concomitant start date is set to the mid-year point (01JULYYYY).

- b. Else if the concomitant month is not missing, the imputed concomitant start date is set to the mid-month point (15MONYYYY).
- 3. If the concomitant start date year value is greater than the study treatment start date year value, the concomitant started after study treatment. Therefore:
 - a. If the concomitant month is missing, the imputed concomitant start date is set to the year start point (01JANYYYY).
 - b. Else if the concomitant month is not missing, the imputed concomitant start date is set to the month start point (01MONYYYY).
- 4. If the concomitant start date year value is equal to the study treatment start date year value:
 - a. And the concomitant month is missing or the concomitant month is equal to the study treatment start date month, then the imputed concomitant start date is set to one day prior to study treatment start date.
 - b. Else if the concomitant month is less than the study treatment start date month, the imputed concomitant start date is set to the mid-month point (15MONYYYY).
 - c. Else if the concomitant month is greater than the study treatment start date month, the imputed concomitant concomitant start date is set to the month start point (01MONYYYY).

If complete (imputed) concomitant end date is available and the imputed concomitant start date is greater than the (imputed) concomitant end date, then imputed concomitant start date should be set to the (imputed) concomitant end date.

5.1.3 Medical history date of diagnosis imputation

Completely missing dates and partially missing end dates will not be imputed. Partial dates of diagnosis will be compared to the treatment start date.

- If DIAG year < study treatment start date year and DIAG month is missing, the imputed DIAG date is set to the mid-year point (01JULYYYY)
- Else if DIAG month is not missing, the imputed DIAG date is set to the mid-month point (15MONYYYY)
- If DIAG year = study treatment start date year and (DIAG month is missing OR DIAG month is equal to study treatment start month), the imputed DIAG date is set to one day before study treatment start date

5.1.4 Other imputations

5.1.4.1 Age

The age of patients with a completely missing date of birth will be set to missing. If a patient's date of birth is partially missing then

- If the year is missing then the age will be set to missing
- Else if the month is missing then the day will be set to 01 and the month will be set to July
- Else if the day is missing then the day will be set to 15.

If a patient has a partially missing date of birth and an imputed age of 17 years then this will be set at 18 years. However, if the imputed age were 16 years then the imputed age will remain at 16 years.

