5.1 Patient population

The study population will consist of patients aged 10 years or older, male or female with transfusion-dependent thalassemia or MDS at very low, low or intermediate risk recruited at all Region Europe participating sites that have completed the 24-week treatment under protocol CICL670F2201 and who have been randomized to the FCT formulation or to the DT formulation. Patients who will have withdrawn prematurely from CICL670F2201 will not be enrolled. Patients with a lag period between completion of CICL670F2201 and enrollment in this study can still be enrolled even if they had to switch to DT or other chelation therapy in this period, following washout.

The investigator or designee must ensure that only patients who meet all the following inclusion and none of the exclusion criteria are offered treatment in the study.

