5.2 Inclusion criteria

Patients eligible for inclusion in this study have to meet all of the following criteria:

- Have completed 24-weeks of study treatment as described in protocol CICL670F2201.
- Are deemed to be tolerating deferasirox treatment by the investigator.
- Provided written informed consent/assent before any study-specific procedures are performed. For pediatric patients, consent will be obtained from parent(s) or legal patient's representative. Investigators will also obtain assent of patients according to local, regional or national guidelines.
- Are deemed to be tolerating deferasirox treatment by the investigator if continuing directly from protocol CICL670F2201.

The inclusion criteria in study CICL670F2201 were stated as follows:

- 1. Written informed consent/assent before any study-specific procedures. For pediatric patients, consent will be obtained from parent(s) or legal patient's representative. Investigators will also obtain assent of patients according to local, regional or national guidelines.
- 2. Male and female patients aged ≥ 10 years
- 3. Patients with transfusion-dependent thalassemia and iron overload, requiring deferasirox DT at doses of ≥ 30 mg/kg/day as per the investigator's decision, OR

Patients with very low, low or intermediate (int) risk myelodysplastic syndrome (MDS) and iron overload, requiring deferasirox DT at doses of ≥ 20 mg/kg/day as per the investigator's decision.

- The very low, low or intermediate (int) risk MDS should be determined by the Revised International Prognostic Scoring System (IPSS-R) and IPSS-R must be confirmed by a bone marrow examination within 6 months prior to study entry and must be hematologically stable with a patient's life expectancy of at least 1 year.
- 4. History of transfusion of at least 20 packed red blood cells (PRBC) units and anticipated to be transfused with at least 8 units of PRBCs annually during the study
- 5. Serum ferritin > 1000 ng/mL, measured at Screening Visit 1 and Screening Visit 2 (the mean value will be used for eligibility criteria).

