7.2.2.5.2 Clinical chemistry

Clinical chemistry samples will be collected at every visit, as described in the visit evaluation schedule in Table 7-1.

Parameters to be measured will include: alkaline phosphatase, ALT/SGPT, AST/SGOT, bicarbonate, calcium, chloride, serum creatinine, inorganic phosphorus, potassium, sodium, total bilirubin (direct and indirect bilirubin only required if total bilirubin is >1.5 ULN), blood urea nitrogen (BUN) or urea, C-reactive protein (CRP). Also, serum ferritin level will be estimated from the blood serum (Section 7.2.1).

In accordance with the deferasirox label, serum creatinine, creatinine clearance, alkaline phosphatase, ALT/SGPT, AST/SGOT, direct bilirubin, indirect bilirubin, total bilirubin would have been assessed in duplicate before the initiation of therapy in the CICL670AIC04 study to establish a reliable pretreatment Baseline.

Creatinine clearance will be estimated using the Cockcroft-Gault equation or Schwartz formula for pediatric patients. This estimate will be provided each time serum creatinine is collected.

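### For a partially missing birth date, the SAP resets an imputed age of 17 to 18 in a trial open from age 10, so likely minors are tabulated as adults at baseline

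*SAP*

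**What the plan says.** SAP 5.1.4.1 (Age) sets out how age is obtained when the date of birth is incomplete. A missing year gives a missing age. If the year is known but the month is not: "Else if the month is missing then the day will be set to 01 and the month will be set to July". If only the day is unknown: "Else if the day is missing then the day will be set to 15".

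The section then adds a further step for a patient whose birth date is incomplete and who has "an imputed age of 17 years then this will be set at 18 years". The next sentence limits it: "However, if the imputed age were 16 years then the imputed age will remain at 16 years". The SAP gives no reason for treating the two ages differently. A patient with a complete date of birth is not touched by any of this.

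Protocol 5.1 defines who can be in the trial: "The study population will consist of patients aged 10 years or older, male or female". The feeder-study criteria repeated in Protocol 5.2 agree: "Male and female patients aged ≥ 10 years". Protocol 10.2 and SAP 2.4.2 both tabulate baseline age with < 18 as the lowest category and 18 to < 50 as the next.

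On creatinine clearance, Protocol 7.2.2.5.2 says: "Creatinine clearance will be estimated using the Cockcroft-Gault equation or Schwartz formula for pediatric patients". Protocol 10.5.2.2 names the same two formulas. Neither section gives an age limit for the paediatric formula or says where the age comes from.

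**The concern.** Raising 17 to 18 would make sense where no one under 18 can be enrolled, because an imputed 17 would then have to be an artefact of the imputation. That is not the case here. Seventeen is an eligible age, the protocol provides for assent from paediatric patients, and the baseline table has a row for minors.

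The rule is also one-sided. It acts only on the value just below the 18-year boundary and only upwards. An imputed 16 stays 16, so the SAP accepts that imputed minors can exist, and then overrides the one imputed age at which the override changes the category.

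At stake is the accuracy of the age description: the count in the < 18 row, the count in the 18 to < 50 row, the continuous age summary and the listed ages.

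**Working it through.** The plan gives no figure to reproduce here, so the check is to apply the SAP rule and see how often the reset is right.

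**Inputs from the documents**
- Month missing: birth date imputed as 1 July of the birth year (SAP 5.1.4.1).
- Day missing: birth date imputed as the 15th of the birth month (SAP 5.1.4.1).
- Imputed 17 becomes 18; imputed 16 stays (SAP 5.1.4.1).
- Category boundary at 18 (Protocol 10.2, SAP 2.4.2).
- Planned maximum enrolment of 58 (SAP Section 3).

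**Assumptions not in the documents**
- True birth dates are uniform over a 365-day year.
- The date at which age is computed is uniform over all dates on which the imputed age is 17.

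This gives 365 × 365 = 133,225 equally likely pairs of birth date and reference date for each type of missing data.

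**Month missing (1 July imputed)**
- True age is 18 if the patient was born before 1 July and the reference date falls between the true 18th birthday and the imputed one. There are 181 such birth dates, contributing 1 to 181 reference days each: 181 × 182 / 2 = 16,471 pairs. 16,471 / 133,225 = 12.4%.
- True age is 16 if the patient was born after 1 July and the reference date precedes the true 17th birthday. There are 183 such birth dates: 183 × 184 / 2 = 16,836 pairs. 16,836 / 133,225 = 12.6%.
- True age is 17 in the rest: 75.0%.
- Truly under 18: 12.6% + 75.0% = 87.6%, about 88%.

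**Only the day missing (15th imputed)**
- True age is 18 if born on days 1 to 14: 14 + 13 + … + 1 = 105 pairs per month, and 12 × 105 = 1,260. 1,260 / 133,225 = 0.95%, about 1%.
- True age is 16 if born after the 15th: 136 pairs in each of seven 31-day months, 120 in each of four 30-day months and 91 in February. 7 × 136 + 4 × 120 + 91 = 1,523. 1,523 / 133,225 = 1.1%.
- True age is 17 in the rest: 97.9%.
- Truly under 18: about 99%.

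A direct enumeration of all date pairs gave the same proportions.

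**Share placed on the wrong side of 18**

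| Missing part | With the reset | Keeping the imputed 17 |
|---|---|---|
| Month (and day) | about 88% | about 12% |
| Day only | about 99% | about 1% |

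**Weight of one patient.** 1/58 = 1.7% of the planned maximum. Adding one year to one patient's age would move the mean of 58 patients by 1/58 = 0.017 years, so the category counts are where a change could be seen.

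**Where the derived age is used.** SAP Section 4 removes the age subgroup analyses, and the document history shows that the by-age tables for tablet consumption, adverse events and adverse events of special interest went with them. What remains is the baseline summary of age (categorical and continuous) and the listings in SAP 2.4.2. No analysis set in SAP 2.2 depends on age, and no hypothesis is tested.

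**The case against.** The strongest case on the other side is about reach, and most of it stands.

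- The rule applies only to partial birth dates. The documents do not say how many patients have one, or how many patients are minors. The number reset could be zero.
- The age subgroups have gone, so no planned safety or efficacy comparison by age can be distorted. A reader might infer that adverse events in minors would be misreported by age group; under SAP Amendment 1 no such tables are planned.
- Not every reset is wrong. On the calculation above, about 1% to 12% of the patients reset are truly 18.
- The SAP does not say why the rule was written. That it suits an adult-only trial is an inference, and nothing shows intent.

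A stronger reading is tempting: that the reset switches a patient from the Schwartz to the Cockcroft-Gault formula and so affects creatinine clearance, a primary laboratory variable. The documents do not support this as a finding. It needs two things that they do not state: that the SAP-derived age feeds the formula, and that paediatric means under 18. Protocol 7.2.2.5.2 has an estimate supplied with every serum creatinine, Table 7-2 lists clearance in the local laboratory plan, and Table 7-1 marks it as a database item at each visit. All of that is compatible with a value calculated outside the analysis from the patient's actual age. Protocol 10.5.2.2 describes the estimation within the analysis section, so the question is open either way.

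None of this supplies a reason to keep the reset.

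**Conclusion.** The point holds as a small descriptive error. For a partially missing date of birth, the SAP replaces an imputed 17, a valid age in this trial, with 18, and so moves the patient out of the < 18 baseline category. Under uniform birth and reference dates the reset puts the patient in the wrong category about 88% of the time when the month is missing and about 99% of the time when only the day is missing. Other date distributions would change these percentages.

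The demonstrated consequence is limited to the baseline age summaries and listings, for an unknown and possibly zero number of patients, each 1.7% of the planned maximum of 58. The primary and secondary analyses are not shown to be affected. The link to creatinine clearance is a matter to clarify and should not be reported as an error. The change is worth making because it is simple, but nothing in the trial's conclusions is shown to turn on it.

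**What to change.** In SAP 5.1.4.1, delete the sentence that changes an imputed 17 to 18, and the sentence on age 16, which then has no purpose. Use the imputed age as it stands in the baseline age table and listings.

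Separately, and as a clarification only, add a line stating which age (recorded by the site or derived under the SAP) and which paediatric cut-off decide between the Schwartz and Cockcroft-Gault formulas. The choice of cut-off is for the sponsor.

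The cost is two deleted sentences and one added line. No planned analysis is lost and no further data are needed.

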5.1.4.2 Dose interruptions, dose delays, and dose changes

This section provides additional details to those included in Section 2.5.1.

Dose interruption

A dose interruption will be indicated in the eCRF by a dosing record with an actual total daily dose of 0 mg for one or more days. In order not to over count interruptions, dosing records with 0 mg entered as last dosing record will not be counted as interruptions. Those represent the reason for permanent discontinuation and will therefore be presented in the reason for treatment discontinuation analysis.

Dose reduction

A reduction is defined as a decrease from the previous non-zero dose. For example, in the sequence of planned dose (mg/kg/day) 25-0-15, the 15 mg/kg/day dose will be counted as a reduction. The planned zero dose is also counted as a dose reduction record. The reduction will be determined using the eCRF 'planned dose'. If the planned dose is reduced as described above, a reduction will be counted.

5.2 Statistical models

Clopper Pearson CI

5.3 Rule of exclusion criteria of analysis sets

Table 5-1 Protocol deviation categories used

PD Category	PD Code
Eligibility	E
Discontinuation of treatment/ study	D
Prohibited Concomitant Medication	M
Study drug (incorrect dose, wrong treatment)	S
Other	O

The full list of PDs are defined in the data review plan (DRP) which is located in the document management system in the following folder:

• 'CREDI Projects/I/ICL670A/CREDI Studies/ICL670AIC04/Administrative Files (study level)/Validation and Planning documents'

Table 5-2 Patient classification

Analysis Set	PD ID that	Non-PD criteria that cause
	cause patients to be excluded	patients to be excluded
FAS	103	Not enrolled
SAF	103, D05	Not in FAS;
		No study drug taken during the study;
		Not having at least one post-baseline safety assessment on or after Visit 3 (Day 1)

6 References

Cheng WJ et al (2018) Adherence to iron chelation therapy in patients who switched from deferasirox dispersible tablets to deferasirox film-coated tablets. Current Medical Research and Opinion; DOI: 10.1080/03007995.2018.1470500

